13.6 Analysis of Secondary Endpoints

The secondary endpoints are:

- To evaluate the rates of CR with IVEN in participants with symptomatic treatment naïve WM at 6, 12 and 24 cycles of therapy.
- To evaluate the best overall response to IVEN in participants with symptomatic, treatment naïve WM.
- To evaluate the rate of VGPR at 30 months post treatment initiation. To evaluate median time to response, median time to major response and median time to VGPR to IVEN in participants with symptomatic, treatment naïve WM.
- To evaluate the 24-, 36-, 48-, 60-month Progression Free Survival (PFS) of IVEN in participants with symptomatic treatment naïve WM.
- To evaluate the overall survival of participants treated with IVEN
- To evaluate the time to next treatment with IVEN
- To evaluate the effect of IVEN in the bone marrow burden of disease in participants with symptomatic treatment naïve WM.
- To evaluate the impact of CXCR4 mutations on response to IVEN in participants with symptomatic treatment naïve WM.
- To evaluate the safety profile of IVEN in participants with symptomatic treatment naïve WM.
- To evaluate the impact of IVEN in the participants' QOL.

Continuous variables will be presented as medians and interquartile ranges. Categorical variables will be presented as numbers and proportions. Responses will be defined based on the criteria established by the 6th International Workshop on WM. Secondary outcomes will include the rate of VGPR at 30 months from treatment initiation, and the rate of progression-free survival (PFS) at 24, 36, 48 and 60 months from initiation of study treatment. Overall survival will also be evaluated as a secondary endpoint.

PFS analysis will be performed using the Kaplan-Meier methodology, and participants will be censored at the time of last relevant assessment if they have not demonstrated the event of interest by the end of the study. Interim analyses for safety and efficacy will be performed when 15 patients had completed 6 and 12 months of study treatment.

In recent studies, the MYD88 and CXCR4 mutational status are predictive of clinical status, response to therapy and survival outcomes (Cao 2013, Treon 2013, Treon 2014). Activating MYD88 as well as nonsense and frameshift WHIM-like CXCR4 somatic mutations are common in Waldenström macroglobulinemia. CXCR4 nonsense mutations are present in aggressive cases including hyperviscosity syndrome, and MYD88 status is a determinant of survival. The MYD88 L265P mutational analysis by allele-specific PCR and CXCR4 mutational analysis by Sanger sequencing will be performed by the Bing Center for Waldenström Macroglobulinemia in Boston, MA.

13.7 Reporting and Exclusions

13.7.1 Evaluation of Toxicity

All participants who receive at least one dose of any test material during the study will be included in the safety analysis.

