1. OBJECTIVES

1.1 Study Design

This is a single-arm open-label Phase II study to evaluate the safety and efficacy of Ibrutinib combined with Venetoclax (IVEN) in symptomatic, treatment naive WM patients. Treatment will be administered daily to participants with WM, and participants will receive treatment for 24 28-day cycles. During the first cycle of therapy, participants will initiate Ibrutinib alone therapy, followed by dose escalation starting on Cycle 2 Day 1 to the target dose of Venetoclax with TLS prophylaxis. After a maximum of 24 cycles of therapy participants will discontinue ibrutinib and venetoclax and enter follow-up for 4 years or death.

A Screening visit will be conducted 30 days prior to Cycle 1, Day 1 of study drug administration. At the Screening visit, a medical history will be obtained, and a complete physical examination will be performed including vital signs and an ECOG performance status. A bone marrow aspirate and biopsy, and CT scanning of the chest, abdomen and pelvis will be done. Bone marrow and CT scans will not be repeated if collected within 90 days prior to Cycle 1 Day 1 visit. Clinical laboratory tests including a complete blood count plus differential, comprehensive chemistry panel (electrolytes, BUN, creatinine, albumin, total protein, total bilirubin, SGOT (AST), SGPT (ALT), alkaline phosphatase), magnesium, beta-2-microglobulin, serum and protein electrophoresis with quantification of immunoglobulins (IgM, IgG, IgA) and immunofixation studies, Von Willebrand factor, ristocetin cofactor and FVIII level, HIV, HBsAg, HBsAb, HBcAb and HCV antibody. Serum pregnancy tests for women of childbearing potential will also be performed at the Screening visit. Cryoglobulins and cold agglutinins will be obtained if clinically indicated. Coagulation studies (PT, PTT, PT-INR) and tumor lysis laboratories (calcium, phosphorus, LDH, and uric acid) will also be performed at baseline. .

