5.2 Pre-Treatment Criteria

Cycle 1 Day 1 results do not need to meet eligibility parameters. Day 1 chemistry and hematology laboratories must be reviewed prior to treatment.

Participants must meet the following criteria on Day 1 of cycles with clinic visits (i.e. 1, 2, 3, 4, 7, 10, etc.). For venetoclax dose escalation days during Cycle 2, all below criteria must be met except for the neutrophil count (refer to section 6.2):

- No grade 3 or 4 nausea, vomiting, or diarrhea (if persistent despite optimal antiemetic and/or antidiarrheal therapy)
- No grade 4 or unmanageable nonhematologic grade 3 toxicities
- Neutrophil count $\geq 500/ \text{mm}^3$ (growth factor permitted)
- Platelet count $\geq 50,000/ \text{mm}^3$ in the presence of bleeding (platelet transfusion permitted, including on day of treatment)
- Platelet count $\geq 25,000 \text{ mm}^3$ without bleeding (platelet transfusion permitted, including on day of treatment)

5.2.1 Cycle 1 Day 1

Participants will begin ibrutinib 420 mg PO QD on Cycle 1 Day 1 and continue it as a single agent for 4 weeks to mitigate the risk of tumor lysis syndrome (TLS). Participants will self-dose ibrutinib on an outpatient basis.

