11.1 Antitumor Effect – Hematologic Tumors

11.1.1 Definitions

Evaluable for toxicity: All participants who receive at least one dose of study treatment will be evaluable for toxicity from the time of their first treatment.

Evaluable for response: Only those participants who have measurable disease present at baseline, have received at least one cycle of therapy, and have had their disease re-evaluated will be considered evaluable for response. These participants will have their response classified according to the definitions stated below. (Note: Participants who exhibit objective disease progression or die prior to the end of cycle 1 will also be considered evaluable.)

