13. STATISTICAL CONSIDERATIONS

This is a single-arm open-label Phase II study to evaluate the safety and efficacy of Ibrutinib combined with Venetoclax (IVEN) in symptomatic, treatment naïve WM patients.

Study treatment for all participants was terminated by the Sponsor-Investigator in March of 2022 due to 4 events of ventricular arrhythmia. As of 4/1/22 all participants were notified and instructed to stop study treatment and accrual was permanently discontinued.

13.1 **Study Design/Endpoints**

The primary endpoint of the current study is:

- To evaluate the rate of VGPR or better of the combination Ibrutinib + Venetoclax (IVEN) in participants with symptomatic, treatment naïve WM, within 24 months of therapy.

13.2 **Sample Size, Accrual Rate and Study Duration**

Following a Fleming’s one step approach, and assuming a null (H0) VGPR or better rate of 25% (based on previous experience on single-agent ibrutinib efficacy in previously untreated patients with WM), and an alternative (H1) VGPR rate of 45%, a total of 50 evaluable patients need to be accrued to show the proposed difference with an alpha (2-sided type I error) of 0.03 and a power (1-beta or type II error) of 87%. Assuming 10% drop out or unevaluable rate, up to 55 participants will be enrolled. If 19 or more participants obtain a VGPR then the combination of ibrutinib and venetoclax warrants further evaluation. If fewer than 19 participants obtain a VGPR, the combination should not continue further evaluation.

Accrual Targets					
Ethnic Category	Sex/Gender				
	Females		Males		Total
Hispanic or Latino	2	+	6	=	8
Not Hispanic or Latino	10	+	32	=	42
Ethnic Category: Total of all participants	12 (A1)	+	38 (B1)	=	50 (C1)
Racial Category					
American Indian or Alaskan Native		+		=	
Asian		+	1	=	1
Black or African American	1	+	1	=	2
Native Hawaiian or other Pacific Islander		+		=	
White	11	+	36	=	42
Racial Category: Total of all participants	12 (A2)	+	38 (B2)	=	50(C2)
	(A1 = A2)		(B1 = B2)		(C1 = C2)

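### Section 13 plans adverse-event summaries only as counts and proportions in all dosed participants, and was not adapted to the March 2022 stop; analyses by treatment period and exposure should be added

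*Combined protocol and SAP*

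**What the plan says.** The safety objective in Section 13.6 concerns the combination: "To evaluate the safety profile of IVEN in participants with symptomatic treatment naïve WM". Under Section 1.1, "participants will initiate Ibrutinib alone therapy, followed by dose escalation starting on Cycle 2 Day 1". Section 5.1 caps ibrutinib at 24 cycles and venetoclax at 23.

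The safety population in Section 13.7.1 is everyone dosed: "All participants who receive at least one dose of any test material during the study will be included in the safety analysis". Section 11.1.1 agrees: "All participants who receive at least one dose of study treatment will be evaluable for toxicity from the time of their first treatment". Section 7 collects adverse events from the start of treatment to 30 days after the last dose.

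On method, Section 13.6 says "Categorical variables will be presented as numbers and proportions". Section 13.5 repeats that sentence. Time-to-event methods and censoring appear only for progression: "PFS analysis will be performed using the Kaplan-Meier methodology". Section 13.6 also mentions interim safety analyses but names no adverse-event method for them.

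Section 13 opens with the early stop: "Study treatment for all participants was terminated by the Sponsor-Investigator in March of 2022 due to 4 events of ventricular arrhythmia". Section 1.1 adds that two of the first three such events were fatal. Nothing later in Section 13 says how shortened exposure will be handled in the safety analysis.

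**The concern.** Two questions matter most for a trial that ended on a safety signal, and the planned summaries answer neither.

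1. **How large is the risk over the course as planned?** A stop on one calendar date cuts later entrants short more than earlier ones. Because reporting ends 30 days after the last dose, their observed time at risk ends early as well. A simple proportion gives a participant stopped after two cycles the same weight as one who completed 24. The plan allows for incomplete follow-up when it analyses progression but not when it analyses adverse events.

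2. **Did events arise before or after venetoclax was added?** Section 7.1.1.2 already lists ventricular tachyarrhythmia, some of it fatal, as a reported risk of ibrutinib. Timing relative to the first venetoclax dose is therefore an obvious thing to report. Section 7.2 defines attribution against study treatment as a whole, so attribution does not fill this gap. Section 13.5 foresees participants who leave before Cycle 2 Day 1. They would count in the denominator for the combination without having taken it.

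**Working it through.** The plan states no adverse-event rate, exposure total or safety precision, so there is no figure to reproduce.

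**Inputs from the documents:** 4 ventricular arrhythmia events (Section 13); a 24-cycle course of 28-day cycles (Section 5.1); a 30-day reporting window after the last dose (Section 7); 50 evaluable and up to 55 enrolled as planned (Section 13.2).

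**Assumptions:** N treated = 50; 4 events in 4 different participants; constant hazard; mean cycles received m = 6, 12, 18 or 24.

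**Step 1, crude proportion.** 4/50 = 8.0%, exact 95% interval 2.2% to 19.2%.

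**Step 2, projected 24-cycle risk.** Risk = 1 − exp(−24 × 4 / person-cycles). Person-cycles are 50 × m without the reporting window. With it they are 50 × (m + 30/28), that is, 1.07 cycles more per person. Intervals use the exact Poisson limits for 4 events, 1.09 and 10.24, with N and m held fixed.

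| Mean cycles | Risk without window (95% interval) | Risk with window (95% interval) |
|---|---|---|
| 6 | 1 − exp(−96/300) = 27.4% (8.3 to 55.9) | 1 − exp(−96/353.6) = 23.8% (7.1 to 50.1) |
| 12 | 1 − exp(−96/600) = 14.8% (4.3 to 33.6) | 1 − exp(−96/653.6) = 13.7% (3.9 to 31.3) |
| 18 | 1 − exp(−96/900) = 10.1% (2.9 to 23.9) | 1 − exp(−96/953.6) = 9.6% (2.7 to 22.7) |
| 24 | 1 − exp(−96/1200) = 7.7% (2.2 to 18.5) | 1 − exp(−96/1253.6) = 7.4% (2.1 to 17.8) |

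With the window counted, as it should be because events are collected there, every interval includes 8.0%. Without it, only the 6-cycle interval starts above 8.0%, at 8.3%.

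**Step 3, other values of N (no window).** With 30 treated, the crude figure is 13.3% and the projections are 41.3%, 23.4%, 16.3% and 12.5%. With 55 treated, it is 7.3% against 25.2%, 13.5%, 9.2% and 7.0%. If the 4 events fell in 3 of 50 participants, the crude figure would be 3/50 = 6.0%.

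**Step 4, effect of the lead-in on the proportion.** Cycle 1 events can only add to the numerator of an any-time incidence. The proportion falls only through participants who never took venetoclax. If k of 50 are of this kind and had no event, the figure among venetoclax recipients is 4/(50 − k): 8.2% for k = 1, 8.5% for k = 3 and 8.9% for k = 5. These shifts are small against the interval of 2.2% to 19.2%.

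**The case against.** The all-treated set is the conventional safety population, and the lead-in is part of the regimen, so counting from the first dose is proper. A reader might infer that Section 13.7.1 defines the wrong population. It does not, and the set should stay.

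A reader might also infer that Cycle 1 dilutes the safety profile of the combination. For a crude incidence that is largely wrong, as Step 4 shows. The gap is that the periods are not shown separately.

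The sentence on numbers and proportions is general, does not name adverse events and does not rule out further tables. Nothing in the plan presents a proportion as a 24-cycle risk. This stands, but the plan commits to nothing better.

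The direction of any bias is not established. The documents give no accrual dates, cycles received or event dates, so unequal exposure is an inference from staggered entry and a common stop date. If the arrhythmia hazard lay only in the first six cycles and everyone completed six, the crude figure would already equal the full-course risk. Stopping because events had occurred can also bias the observed rate upward.

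Finally, safety is a descriptive secondary objective with no decision rule attached, and treatment has already ended. The protocol's own background safety data for venetoclax (Section 7.1.1.1) are crude percentages, so a crude table remains useful for comparison. These points limit the severity but do not remove the gap.

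**Conclusion.** The point holds as a gap in the analysis plan. Section 13 has no adverse-event summary by treatment period, no person-time rate and no cumulative incidence, and its safety analysis was not revised for the stop. A crude proportion from this trial cannot be read as the risk of the planned course of ibrutinib plus venetoclax, and it may understate that risk.

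Under the stated assumptions for 50 treated, the projected risk ranges from about three times the crude 8.0% at a mean of 6 cycles to no gap at 24. A reader might take the 12-cycle projection as evidence that the true risk is nearly double the crude figure (14.8/8.0 = 1.85). The documents do not support that. It rests on an assumed N, mean exposure, constant hazard and one event per participant, and its interval contains 8.0%. The remedy is inexpensive and the safety result is central to this trial, so the change is worth making. The planned all-treated table remains valid as a description of what was observed.

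**What to change.** In Sections 13.6 and 13.7.1:

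- Keep the all-treated safety set and its table.
- Add adverse-event tables for two periods: Cycle 1 on ibrutinib alone, and from the first venetoclax dose to 30 days after the last dose. The denominator for the second is participants who took venetoclax.
- For ventricular arrhythmia, other cardiac events of grade 3 or higher, and death, report rates per person-time over the adverse-event window with exact Poisson intervals.
- For the same events, report cumulative incidence by cycle, censored at the end of each participant's adverse-event window. Treat death from other causes as a competing event for the non-fatal endpoints.
- State the number treated, the distribution of cycles received, and the cycle in which each arrhythmia occurred.

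No new data should be needed. The study calendar in Section 10 has adverse events monitored at the treatment visits and both drugs recorded by cycle. The cost is some wording and a few tables. Intervals will be wide, few participants may remain at risk in late cycles, and the reported figure may be less favourable.

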13.7.2 Evaluation of the Primary Efficacy Endpoint

All participants who have completed at least 4 weeks of protocol therapy will be included in the evaluation of primary efficacy endpoint. Each participant should be assigned a response category based on the response criteria in Section 11.1.2.

14. PUBLICATION PLAN

The results should be made public within 12 months of reaching the end of the study. The end of the study is the time point at which the last data items are to be reported, or after the outcome data are sufficiently mature for analysis, as defined in the section on Sample Size, Accrual Rate and Study Duration. If a report is planned to be published in a peer-reviewed journal, then that initial release may be an abstract that meets the requirements of the International Committee of Medical Journal Editors. A full report of the outcomes should be made public no later than three (3) years after the end of the study.

APPENDIX A PERFORMANCE STATUS CRITERIA

ECOG Performance Status Scale		Karnofsky Performance Scale	
Grade	Descriptions	Percent	Description
0	Normal activity. Fully active, able to carry on all pre-disease performance without restriction.	100	Normal, no complaints, no evidence of disease.
		90	Able to carry on normal activity; minor signs or symptoms of disease.
1	Symptoms, but ambulatory. Restricted in physically strenuous activity, but ambulatory and able to carry out work of a light or sedentary nature (e.g., light housework, office work).	80	Normal activity with effort; some signs or symptoms of disease.
		70	Cares for self, unable to carry on normal activity or to do active work.
2	In bed <50% of the time. Ambulatory and capable of all self-care, but unable to carry out any work activities. Up and about more than 50% of waking hours.	60	Requires occasional assistance but is able to care for most of his/her needs.
		50	Requires considerable assistance and frequent medical care.
3	In bed >50% of the time. Capable of only limited self-care, confined to bed or chair more than 50% of waking hours.	40	Disabled, requires special care and assistance.
		30	Severely disabled, hospitalization indicated. Death not imminent.
4	100% bedridden. Completely disabled. Cannot carry on any self-care. Totally confined to bed or chair.	20	Very sick, hospitalization indicated. Death not imminent.
		10	Moribund, fatal processes progressing rapidly.
5	Dead.	0	Dead.

APPENDIX B. CHILD-PUGH SCORE FOR SUBJECTS WITH LIVER IMPAIRMENT

Measure	1 point	2 points	3 points
Total bilirubin, $\mu\text{mol/L}$ (mg/dL)	<34 (<2)	34-50 (2-3)	>50 (>3)
Serum albumin, g/L (g/dL)	>35 (>3.5)	28-35 (2.8-3.5)	<28 (<2.8)
PT/INR	<1.7	1.71-2.30	>2.30
Ascites	None	Mild	Moderate to Severe
Hepatic encephalopathy	None	Grade I-II (or suppressed with medication)	Grade III-IV (or refractory)

Points	Class
5-6	A
7-9	B
10-15	C

Source:

APPENDIX C. DEFINITIONS OF LABORATORY AND CLINICAL TUMOR LYSIS SYNDROME

Metabolic Classification of Abnormality Syndrome	Criteria for Classification of Laboratory Tumor Lysis Syndrome	Criteria for Clinical Tumor Lysis
Hyperuricemia	Uric acid > 8.0 mg/dl (475.8µmol/liter) in adults or above the upper limit of the normal range for age in children	
Hyperphosphatemia	Phosphorus > 4.5 mg/dl (1.5mmol/liter) in adults or > 6.5 mg/dl (2.1 mmol/liter) in children	
Hyperkalemia sudden death probably or definitely caused by hyperkalemia	Potassium > 6.0 mmol/liter	Cardiac dysrhythmia or
Hypocalcemia sudden death, irritability muscle twitching,	Corrected calcium < 7.0 mg/dl (1.75 mmol/liter) or ionized calcium <1.12 (0.3 mmol/liter) †	Cardiac dysrhythmia, seizure, neuromuscular (tetany, paresthasias, Carpopedal spasm, Trousseau’s sign, Chvostek’s sign, laryngospasm, or bronchospasm), hypotension, or heart failure probably or definitely caused by hypocalcemia.
Acute kidney injury ‡ creatinine level	Not Applicable	Increase in the serum of 0.3 mg/dl (26.5 µmol/liter) (or a

single value > 1.5 times the upper limit of the age-appropriate normal range if no baseline creatinine measurement is available) or the presence of oliguria, defined as an average urine output < 0.5 ml/kg/hr for 6 hrs

† The corrected calcium level in milligrams per deciliter = measured calcium level in milligrams per deciliter + $0.8 \times (4 - \text{albumin in grams per deciliter})$.

‡ Acute kidney injury is defined as an increase in the creatinine level of at least 0.3 mg per deciliter (26.5 μmol per liter) or a period of oliguria lasting 6 hours or more. By definition, if acute kidney injury is present, the patient has clinical tumor lysis syndrome. Data about acute kidney injury from Levin et al.

Note: In laboratory tumor lysis syndrome, two or more metabolic abnormalities must be present during the same

24-hour period within 3 days before the start of therapy or up to 7 afterward. Clinical tumor lysis syndrome requires the presence of laboratory tumor lysis syndrome plus an increased creatinine level, seizures, cardiac dysrhythmia, or death.

APPENDIX D: MANAGEMENT RECOMMENDATIONS FOR LABORATORY ABNORMALITIES FOR VENETOCLAX FIRST DOSE AND ESCALATION

The following table includes recommendations for the management of laboratory abnormalities in the setting of venetoclax first dose and dose escalation. If laboratory TLS is suspected or confirmed, venetoclax should be stopped until resolution and treatment should be administered per institutional guidelines. Otherwise, additional monitoring will be at the discretion of the investigator and venetoclax may be continued.

Abnormality	Dose Modification and Management recommendation
Laboratory Events	
Hyperkalemia (Including rapidly rising potassium)	

Potassium ≥ 0.5 mmol/L increase from prior value (even if potassium within normal limits [WNL])
 
*Hospitalization at discretion of investigator
 
**If sample is hemolyzed, sample should be re-taken before any intervention is instituted
	
 • Recheck potassium, phosphorus, uric acid, calcium and creatinine in 1-2 hours STAT. If further ≥ 0.2 mmol/L increase in potassium, but still < upper limit of normal (ULN), manage as per potassium \geq ULN. Otherwise recheck in 1 hour. • Resume per protocol testing if change in potassium is < 0.2 mmol/L, and potassium < ULN, and no other evidence of tumor lysis. • At the discretion of the investigator, may recheck prior to hospitalization. If stable or decreased, and still WNL, hospitalization is at the discretion of the investigator. Potassium, phosphorus, uric acid, calcium and creatinine must be rechecked within 24 hours.

Potassium > upper limit of normal but less than (6 mmol/L) 6 mEq/L and/or asymptomatic
 
*Hospitalization at discretion of investigator
 
**If sample is hemolyzed, sample should be re-taken before any intervention is instituted
	
 • Consider performing ECG. • Consider Kayexalate 60 g (or Resonium A 60 g). • Consider furosemide 20 mg IV \times 1. • If there is ECG/telemetry evidence of life-threatening arrhythmia, the patient should be sent to ED and managed accordingly • Recheck potassium, phosphorus, uric acid, calcium and creatinine STAT within 1-2 hours of intervention. • If potassium < ULN on recheck and no evidence of tumor lysis, resume per protocol. • If potassium > ULN but less than 6 mmol/L 1-2 hours later and no evidence of tumor lysis, treat as potassium > ULN but less than 6 mmol/L. • If potassium >6 mmol/L, the patient should be sent to ED for further management

Potassium ≥ 6.0 mmol/L (6.0 mEq/L) and/or symptomatic (e.g.,
	
 • Perform STAT EKG • The patient should be sent to ED for further

muscle cramps, weakness, paresthesias, nausea, vomiting, diarrhea)
 
*Hospitalization Indicated
 
**If sample is hemolyzed, sample should be re-taken before any intervention is instituted
	
management

Hyperuricemia
	

Uric acid ≥ 8.0 but <10 mg/dL (476 $\mu\text{mol/L}$)
 
*Hospitalization at discretion of investigator
	
 • IVF and recheck • Recheck potassium, phosphorus, uric acid, calcium and creatinine in 1-2 hours STAT.

Uric acid ≥ 10 mg/dL (595 $\mu\text{mol/L}$)
 
OR
 
Uric acid ≥ 8.0 mg/dL (476 $\mu\text{mol/L}$) with 25% increase and creatinine increase ≥ 0.3 mg/dL (≥ 0.027 mmol/L) from pre-dose level
 
*Hospitalization Indicated
	
 • The patient should be sent to ED for further management

Hypocalcemia
	

Corrected Calcium ≤ 7.0 mg/dL (1.75 mmol/L)
 
AND
 
Patient symptomatic (e.g., muscle cramps, hypotension, tetany, cardiac arrhythmias)
 
*Hospitalization Indicated
	
 • The patient should be sent to ED for further management

Hyperphosphatemia
	

Phosphorus ≥ 5.0 mg/dL (1.615 mmol/L) with ≥ 0.5 mg/dL (0.16 mmol/L) increase
 
*Hospitalization at discretion of investigator
	
 • Consider administering a phosphate binder (e.g., aluminum hydroxide, calcium carbonate, sevelamer hydroxide, or lanthanum carbonate). • Recheck potassium, phosphorus, uric acid, calcium and creatinine in 1 hr STAT. If phosphorus <5.0 mg/dL 1-2 hours later and no evidence of tumor lysis, resume per protocol. • Send to ED per clinician judgement

Creatinine
	

Increase $\geq 25\%$ from baseline
	
 • Start or increase rate of IV fluids.

*Hospitalization at discretion of investigator	
• Recheck potassium, phosphorus, uric acid, calcium and creatinine in 1 to 2 hours STAT. Resume per protocol testing if no further $\geq 25\%$ increase.• Send to ED per clinician judgement
--	--
